### **6.3.4 Control of Bias and Confounding**

For Aim 1, patients will be contacted once monthly for symptom reporting. Capture of the primary outcome will be dependent on completion of study visits, phone calls and complete data collection from the medical record. Accordingly, study procedural protocols will be implemented to ensure systematic approach for each enrolled subject. We will also develop a database that will inform a systematic approach to medical record review. This is a descriptive study and thus is not vulnerable to confounding.

To control for possible confounding in the comparison of infection incidence rates of ALL patients to those of healthy control patients, all healthy control patients will be matched to ALL cohort patients based on both age and sex, and controls will be assigned the same one-year “follow-up” period as those of their matched ALL cohort patients, to account for seasonal variation in infection rates as described above. Demographic data and vaccination histories

will be collected as outlined above for both ALL cohort patients and healthy controls to monitor for balance with respect to these important factors. Healthy control patients will be included only if they do not have pre-existing medical conditions that might put them at increased risk for infection to ensure assembly of a healthy cohort that most closely mirrors the general population of healthy children. Further, to reduce the risk of selection bias in the healthy control cohort, a waiver of consent and HIPAA authorization will be requested for these patients.

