## 5 STUDY EVALUATIONS AND MEASUREMENTS

### 5.1 Screening and Monitoring Evaluations and Measurements

#### 5.1.1 Medical Record Review

Variables to be abstracted into the REDCap™ database from the medical charts of ALL cohort patients enrolled at each site will include the following:

- Date of study days
- Weight
- Height
- Demographics (sex, race, ethnicity)
- Underlying conditions (e.g., type of leukemia)
- Co-morbid conditions
- Laboratory values (e.g. Creatinine, AST, ALT, Bilirubin, coagulation profile, WBC, platelets)
- Level of illness (e.g. need for ICU admission, intubation, vasopressors)
- Immune suppression therapies most recently associated with the qualifying condition
- Vital status at last date of follow-up
- Vaccination records
- Social determinants of health-related data (e.g. block group number (zip code plus 4) of residence, insurance type) (Optional – to be collected only for ALL cohort patients/families who consent to having these data collected and for healthy control patients)

Results from the following reports will be collected when available

- Pathology reports
- All radiology reports
- Microbiology results
- Non-culture mycology testing (e.g., Histoplasma urine antigen)
- Interventional radiology reports
- Surgical and procedural reports (e.g. bronchoscopy, eye and sinus exams)

---

Variables to be collected for matched healthy control cohort patients selected from CHOP's PeRC include:

- Date of study days (assigned to mirror the follow-up period of the matched ALL cohort patients)
- Demographics (sex, race, ethnicity, age)
- Underlying conditions
- Co-morbid conditions
- Laboratory values (e.g. Creatinine, AST, ALT, Bilirubin, coagulation profile, WBC, platelets)
- Details of any infection-related healthcare encounters occurring during the assigned study period (e.g. date of infection(s), lab results related to infection, physical examination findings, medications)
- Level of illness (e.g. need for ICU admission, intubation, vasopressors)
- Vaccination records
- Social determinants of health-related data (e.g. block group number (zip code plus 4) of residence, insurance type)

Results from the following reports will be collected when available and related to infections occurring in the study follow-up period:

- Pathology reports
- All radiology reports
- Microbiology results
- Non-culture mycology testing (e.g., Histoplasma urine antigen)
- Interventional radiology reports

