The REDCap™ database has numerous pre-programmed edit checks to ensure complete, consistent and accurate data. These include logical checks, out-of-range checks, missing and completeness checks. After automated checks, the CHOP coordinator will manually verify data consistency and completeness. Discrepancies identified in data review will be queried for clarification. Once entry, review, and resolution of queries have been completed, the database will be closed.

In accordance with CHOP policy A-3-9, all study data, including PHI and the master list, and study-related documents will be maintained for a minimum of 6 years after completion of the study.

Data for matched healthy control patients will be obtained via automated pull from the EHR, supplemented by chart abstraction as needed to capture the same infection event data as is collected for the ALL cohort. REDCap™ will also be used to store data for controls.

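### Aim 1 can find infections by contact in ALL patients but only from CHOP records in controls; the plan does not say whether contact-only events count, and no analysis shows the effect on the rate ratio

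*Combined protocol and SAP*

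**What the plan says.** The comparison with controls is part of the primary objective (section 2.1), and it is the comparison that section 6.4 powers.

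For ALL patients, events can come to light in several ways. Section 6.3.4 states "For Aim 1, patients will be contacted once monthly for symptom reporting" and then "Capture of the primary outcome will be dependent on completion of study visits, phone calls and complete data collection from the medical record". Section 3.2.1 adds calls, texts or emails to caregivers between visits, and section 4.2.1 adds an infection history at baseline and at each follow-up visit.

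For controls, section 7.1 states "Data for matched healthy control patients will be obtained via automated pull from the EHR". It goes on to describe this pull as "supplemented by chart abstraction as needed to capture the same infection event data as is collected for the ALL cohort". Section 7.5 adds that these are existing data, gathered under a waiver after the matched ALL patient has finished follow-up. All controls come from CHOP's consortium, wherever the ALL patient was enrolled (Abstract, Setting/Participants).

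On what counts as an event, the passages do not quite meet. The Abstract (Study Measures) ties Aim 1 to infections documented at an inpatient or outpatient encounter, and Figure 1 says the check-ins collect encounter data. The Abstract (Study Design) has the check-ins look for symptoms as well as documented infections. Section 6.1 admits clinical and microbiologically confirmed infections and counts every unique one. It does not say whether an event known only from contact qualifies, or when repeat encounters form one episode.

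**The concern.** Contact with families can reveal two kinds of event that a CHOP record pull cannot: illness that never reached a clinician, and care given at a facility outside the record. If either kind enters the ALL numerator, nothing equivalent can enter the control numerator. The IRR expected under no true difference is then not 1. An excess, or a null result, could partly reflect how events were found, and the analyses in section 6.3.2 would not show how much. Section 6.4 intends clinicians to use the descriptive and comparative results when they advise families. Section 6.3.4 deals with age, sex, season, pre-existing conditions and selection of controls, but not with unequal detection.

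**Working it through.** **Inputs from the plan.** ALL rate 1.88 per person-year, estimated from this study's own ALL patients; two-sided 0.05; overdispersion φ from 1 to 3; Table 1 based on 50 versus 150 with one year each (all section 6.4). Planned numbers 110 and 330 (section 3.2.2). **Not in the plan:** control capture relative to ALL capture, called s below. Every value of s is an assumption.

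**Step 1: reproduce Table 1.** Take SE(log IRR) = √[φ(1/(n₁r₁) + 1/(n₀r₀))]. For the first row, n₁r₁ = 50 × 1.88 = 94 and n₀r₀ = 150 × 1.30 = 195, so SE = √(1/94 + 1/195) = 0.126. Power = Φ(log(1.88/1.30)/SE − 1.96) = 83.6%.

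| Overdispersion | 1 | 1.5 | 2 | 2.5 | 3 |
|---|---|---|---|---|---|
| Table 1 | 80.1% | 81.0% | 80.1% | 81.2% | 80.0% |
| Closed form | 83.6% | 83.4% | 82.3% | 81.8% | 80.2% |
| Simulation, robust Wald test | 81.8% | 82.0% | 81.0% | 80.6% | 79.1% |

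The plan names no test. Simulation agrees with every row within 2 points, and the closed form is at most 3.5 points high. That is close enough for an illustration.

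**Step 2: effect of unequal capture on the IRR.** Observed IRR = true IRR / s. With a true IRR of 1: s = 0.9 gives 1/0.9 = 1.11; s = 0.8 gives 1/0.8 = 1.25; s = 1.25 gives 1/1.25 = 0.80.

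**Step 3: chance of rejection with a true IRR of 1.** Use the same SE with n₁ = 110, n₀ = 330, r₁ = 1.88 and r₀ = 1.88s, ignoring matching. P(reject) = Φ(|log s|/SE − 1.96) + Φ(−|log s|/SE − 1.96). For s = 0.8 and φ = 1: n₁r₁ = 206.8, n₀r₀ = 330 × 1.504 = 496.3, SE = 0.0828, |log s| = 0.223, ratio 2.70, P = 0.769.

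| s (assumed) | Observed IRR | φ = 1 | φ = 2 | φ = 3 |
|---|---|---|---|---|
| 1.00 | 1.00 | 5% | 5% | 5% |
| 0.90 | 1.11 | 25% | 15% | 12% |
| 0.80 | 1.25 | 77% | 48% | 34% |
| 1.25 | 0.80 | 81% | 52% | 38% |

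A simulation with 4,000 data sets per cell gave 75/48/35% at s = 0.8, 27/15/13% at s = 0.9 and 82/53/38% at s = 1.25. At 50 versus 150, the s = 0.8 row is 44/25/18%. The bias does not shrink as the sample grows; it only becomes easier to call significant.

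**Step 4: cost of a record-only sensitivity analysis.** The IRR detectable with 80% power solves log(IRR) = (1.96 + 0.84) × SE with r₀ = r₁/IRR. With all events (206.8 in ALL patients) it is 1.26/1.40/1.51 at φ = 1/2/3. If 20% of events are excluded (165.4 remain in ALL patients), it is 1.30/1.46/1.60. A subset holding an assumed 30% or 10% of ALL events (62.0 or 20.7) could detect only 1.55 or 2.26, even at φ = 1.

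**Step 5: why any restriction must apply to both groups.** Suppose a true IRR of 1 and 20% of events of the restricted kind in each group. Excluding them from ALL patients only gives 1.00 × (1 − 0.2) = 0.80. Excluding them from both leaves 1.00.

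**The case against.** The strongest reply is that the plan already aligns the groups. The Abstract defines the event by a documented encounter, Figure 1 treats the check-ins as a pointer to encounters, and section 7.1 sets out to obtain the same event data for controls. Most of this stands. A reader might infer that the two groups have different event definitions, or that symptom-only reports will be counted. The documents do not establish either; they leave the status of a contact-only event open. Care outside CHOP remains beyond a CHOP pull whatever the intention.

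A reader might also draw on the lists in section 5.1.1. Control reports carry the condition "Results from the following reports will be collected when available and related to infections occurring in the study follow-up period", and the ALL list alone includes "Surgical and procedural reports (e.g. bronchoscopy, eye and sinus exams". But reports related to infection are the ones that bear on the outcome, nothing shows that the missing line would change a count, and the control list has an item that the ALL list lacks: "Details of any infection-related healthcare encounters occurring during the assigned study period". Likewise, the phrase "study procedural protocols will be implemented to ensure systematic approach for each enrolled subject" might be read as leaving controls out. The following sentence of section 6.3.4 promises systematic record review without that limit, and control data also go into REDCap. Neither argument shows an effect on the rates.

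The planned subsets are a partial answer. Section 6.3.2 reports microbiologically documented and sinopulmonary infections, which should depend less on contact, and its comparison with controls could be read to include them. They are not given the role of a check on ascertainment.

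Direction is a fair objection too. Section 3.3.3 draws controls from patients who had care at CHOP during the period, which may select families who seek care and so raise the control rate.

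**Conclusion.** The concern holds in this limited form. The routes by which events can be found differ between the groups, the plan does not say whether a contact-only event counts in the comparison, and no planned analysis shows the effect on the IRR. The ratio may be biased by an unknown amount, and the direction is uncertain.

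The rejection figures rest wholly on the assumed s, one year of follow-up each and unmatched analysis. They show that modest differences in capture would matter at this sample size. They are not an estimate of this study's error rate, although a reader might take the 77% that way. Nor do the documents support the inference that an excess in ALL patients would be an artefact. The descriptive ALL rate is not affected by this comparison problem. This is a low-cost improvement to make before the control data are drawn, not a reason to doubt the design.

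**What to change.** (a) In sections 6.1 and 6.3.2, state that for the comparison with controls an event is an infection documented at a medical encounter, as the Abstract already says, and that symptom-only reports do not count. State one event rule and one unique-episode rule for both groups, fixed before the control pull. If such rules already exist in study procedures or the data dictionary, cite them and say that they cover controls.

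(b) Flag the source of each event where it can be recovered. Beside the planned IRR, report as a sensitivity analysis an IRR with 95% CI restricted, in both groups, to events in the treating health system's record, with the share excluded in each group. This should not replace the planned comparison: it may drop community-treated infections unequally across seven ALL sites and one control system.

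(c) Report the IRR against controls for the microbiologically documented and antibiotic-treated sinopulmonary subsets as supportive only, given their limited precision.

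(d) In section 6.3.4, name differential ascertainment, of unknown size and direction, as a limitation.

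**Cost.** No new patients, visits or blood samples, and no need for full chart review of every control. Section 6.3.2 places control data collection after ALL follow-up, so the rules can be set first. Section 1.2 says most of the ALL cohort is already enrolled, so some existing events need re-abstraction and their source may not always be recoverable. The sensitivity analysis has fewer events: the detectable IRR rises from 1.26 to 1.30 at overdispersion 1 if 20% are excluded.

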## **2 STUDY OBJECTIVES**

### **2.1 Primary Objective (or Aim)**

Aim 1: To determine the overall infection incidence rate within the first year following completion of therapy for acute lymphoblastic leukemia and compare that rate with the rate of infections occurring in age- and sex-matched healthy control patients during the same time period.

- Sub-aim: To examine infection incidence in patients who received the monoclonal antibody blinatumomab as part of their ALL treatment protocol versus that of patients who did not receive blinatumomab.

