#### **3.3.2 Exclusion Criteria for ALL Cohort**

- 1) Diagnosis of infant ALL
- 2) Evidence of disease relapse
- 3) History of primary immunodeficiency (except related to Down Syndrome)
- 4) History of a stem cell transplant or cellular immunotherapy
- 5) History of prior malignancy or condition requiring chemotherapy other than for current ALL diagnosis.

Subjects that do not meet all the enrollment criteria may not be enrolled. Any violations of these criteria must be reported in accordance with IRB Policies and Procedures.

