#### **3.3.3 Inclusion/Exclusion Criteria for Matched Healthy Controls Cohort**

Matched healthy control patients will be selected based on age- and sex-matching to ALL cohort patients. All healthy patients who received care at the Children's Hospital of Philadelphia beginning in 2022 during the follow-up period that the ALL cohort patients are followed for the study will be eligible for inclusion in the matched cohort.

Patients with a history of any oncologic diagnosis or other condition that could predispose them to a higher risk of infection (e.g., primary immunodeficiency except related to Down syndrome, receipt of chemotherapy or immunomodulating drugs for treatment of any condition, etc.) will be excluded from the healthy controls cohort to ensure a comparator group that mirrors the typical population of healthy children as closely as possible.

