## 6 STATISTICAL CONSIDERATIONS

### 6.1 Primary Endpoint

The primary endpoint for Aim 1 of this study is to determine the incident infection rate in a cohort of subjects in the first year following completion of ALL therapy. Infections will include both clinical and/or microbiologically confirmed infections. All unique infections for a given subject will be captured and included in the final infection rate per person time estimate. Infections will also be reported in subsets of infections such as microbiologically confirmed (i.e., bacteremia, urinary tract infection or pneumonia with a positive sputum culture) or clinically defined infections. Additionally, a specific subset of infections to be described are sinopulmonary infections. This will include a medical encounter for otitis media, sinusitis, or pneumonia for which an antibiotic was prescribed. Infection events for matched healthy control patients will also be captured and used for comparison to the incident infection rate determined for the ALL participants.

The primary endpoint for Aim 2a is the proportion of patients with measles, varicella and pneumococcus antibodies at each study timepoint. Of note, pneumococcal serology results will include 23 serotypes: 1, 2, 3, 4, 5, 6B, 7F, 8, 9N, 9V, 10A, 11A, 12F, 14, 15B, 17F, 18C, 19A, 19F, 20, 22F, 23F, and 33F. Patients with detectable antibody to 50% or more of these serotypes will be considered to have seroprevalence for pneumococcus. This aim will also describe the total IgG levels at each time point at the individual and cohort level. Understanding the total IgG level will inform interpretation of vaccine-specific serology measures.

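### The ALL-versus-healthy-control rate comparison is controlled only for age, sex and calendar window: demographic balance is monitored but never acted on, and infection-prone conditions are screened out more broadly in controls than in ALL patients

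*Combined protocol and SAP*

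**What the plan says.** - **Objective and endpoint.** Section 2.1 sets out to determine the ALL infection rate and "compare that rate with the rate of infections occurring in age- and sex-matched healthy control patients during the same time period". Section 6.1 words the primary endpoint as the ALL rate, with control infections "used for comparison to the incident infection rate determined for the ALL participants".
- **Control of confounding.** Section 6.3.4 states that "all healthy control patients will be matched to ALL cohort patients based on both age and sex" and gives each control the follow-up window of the matched patient. It adds that "Demographic data and vaccination histories" will be collected in both groups "to monitor for balance with respect to these important factors". No step follows if balance is poor.
- **Analysis.** Section 6.3.2 describes the matching and the control window. It names no model, covariate or adjusted estimate for the comparison. Rates by race and other demographics are descriptive reports.
- **Source of patients.** ALL patients come from seven US sites (3.2.2). All controls come from the CHOP Pediatric Research Consortium, whichever site enrolled the matched patient (Abstract, Setting/Participants).
- **Eligibility.** Section 3.3.3 removes controls with any oncologic diagnosis or "other condition that could predispose them to a higher risk of infection". Its examples are primary immunodeficiency (Down syndrome excepted), chemotherapy, and immunomodulating drugs given for any reason. Section 3.3.2 excludes ALL patients for infant ALL, relapse, primary immunodeficiency (same exception), transplant or cellular immunotherapy, and prior malignancy or another condition needing chemotherapy.
- **Data.** Section 5.1.1 lists race, ethnicity and comorbid conditions for both groups. Insurance and block group are listed for all controls but only for ALL families who consent.

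**The concern.** The plan itself treats these demographic factors as relevant to infection. It calls them important, reports rates by race (6.3.2) and runs a survey to inform later study of disparities in infection rates (5.1.3). A seven-site cohort set against one regional network could easily differ in race and ethnicity. Followed as written, the plan would report such a difference in a table and leave the rate comparison unchanged.

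The eligibility rules add a second difference. A child without leukemia who takes an immunomodulating drug, or has some other infection-prone condition, cannot be a control. An ALL patient with the same unrelated condition can be enrolled unless it is on the shorter list in 3.3.2. Down syndrome is permitted in both groups but is not a matching factor, so its frequency may differ.

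The comparison is the only part of the study with a power calculation (6.4). If adjustment is decided only after balance has been looked at, the choice of model can be guided by the data.

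**Working it through.** **1. The plan's own figure.** Section 6.4 states 80.1% power for 1.88 against 1.30 events per person-year (1.88/1.30 = 1.446, given as IRR 1.45), with 50 against 150 patients, two-sided 0.05 and overdispersion 1. A square-root comparison gives 2(√1.88 − √1.30)/√(1/50 + 1/150) − 1.96 = 0.4619/0.1633 − 1.96 = 0.87, or 80.7% power. A pooled-variance score test gives 81.8%, a pooled log-rate test 79.3% and a log-rate Wald test 83.6%. The stated figure therefore reproduces to within about 2 points by three of the four methods. It assumes no confounding.

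**2. What is controlled.** Setting 6.3.2 and 6.3.4 side by side, age and sex are matched and calendar time is aligned. Race, ethnicity and vaccination are monitored. For comorbidity and insurance not even monitoring is stated.

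**3. Where eligibility differs.** Most of the named examples in 3.3.3 have a counterpart in 3.3.2: primary immunodeficiency, malignancy and chemotherapy. Two parts do not: immunomodulating drugs other than chemotherapy, and the open-ended class of other predisposing conditions.

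**4. Demographic imbalance (assumed values).** The documents give no prevalences or covariate rate ratios. For a factor with rate ratio h and prevalence p1 in ALL patients and p0 in controls, the multiplier on the IRR is [1 + p1(h − 1)]/[1 + p0(h − 1)].

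| h | p1 vs p0 | Multiplier | Reversed |
|---|---|---|---|
| 1.2 | 50% vs 30% | 1.10/1.06 = 1.04 | 0.96 |
| 1.2 | 60% vs 30% | 1.12/1.06 = 1.06 | 0.95 |
| 1.5 | 50% vs 30% | 1.25/1.15 = 1.09 | 0.92 |
| 1.5 | 60% vs 30% | 1.30/1.15 = 1.13 | 0.88 |

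**5. One-sided comorbidity (assumed values).** If a proportion c of ALL patients has a condition that would bar a control, and it multiplies infections by h, the multiplier is 1 + c(h − 1). The low end is 1 + 0.05 × 0.5 = 1.025, the middle 1 + 0.075 × 1 = 1.075 and the high end 1 + 0.10 × 2 = 1.20.

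**6. What a multiplier of that size would do.** An observed IRR of 1.45 corresponds to 1.45/1.10 = 1.32 or 1.45/1.20 = 1.21 once a bias of 1.10 or 1.20 is removed, and to 1.45/0.90 = 1.61 if the bias ran the other way.

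With the planned 110 against 330, suppose the true IRR is 1, the bias is b and the control rate is λ. The expected test statistic is ln b divided by √{φ[1/(110λb) + 1/(330λ)]}, where φ is the overdispersion. Taking λ from 0.99 to 1.30 (the extremes of Table 1), a nominal 5% test rejects as follows:
- b = 1.10: 15-18% at φ = 1, 8-9% at φ = 3.
- b = 1.20: 42-52% at φ = 1, 17-21% at φ = 3.

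**7. Room for the extra terms.** Expected events are 110 × 1.88 = 207 in ALL patients, and between 330 × 0.99 = 327 and 330 × 1.30 = 429 in controls. That is enough for a few covariate terms.

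**The case against.** The healthy comparator is deliberate. Section 3.3.3 wants controls that resemble typical healthy children, and 6.4 says the results are for managing family expectations. On that reading, survivors with other conditions belong in the ALL group, and removing them answers a different question. This stands: it is why the restricted analysis should be a sensitivity analysis, and why making the adjusted IRR replace the matched one would be a matter of preference.

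Several stronger readings are tempting, and the documents do not support them:
- *That insurance and comorbidity are monitored too.* The sentence in 6.3.4 covers demographics and vaccination only, and insurance is optional for ALL families.
- *That ALL patients keep every condition barred in controls.* Section 3.3.2 already excludes primary immunodeficiency, prior malignancy and other conditions needing chemotherapy, so the asymmetry is narrower.
- *That model terms would remove all the confounding.* Controls have almost no infection-prone comorbidity by design, so there is no overlap to adjust on and only restriction helps. Race and ethnicity terms would not remove site and network differences.
- *That the primary endpoint is a biased rate ratio.* Section 6.1 makes it the ALL rate, which this point does not touch. The comparison is in the primary objective, and the IRR appears only in 6.4.

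The magnitudes are also wholly assumed, and the larger ones need extreme inputs. The objection does not answer the main omission: an imbalance in factors the plan calls important would change nothing in the analysis.

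**Conclusion.** The point holds as a cheap improvement. The comparison rests on matching for age, sex and calendar window, no analysis responds to demographic imbalance, and the control exclusions are broader than the ALL exclusions. Demographic imbalance could move the IRR either way. The eligibility asymmetry would tend to raise it.

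The size cannot be determined from the documents. The ranges of 0.88-1.13 and 1.025-1.20 depend entirely on the assumed prevalences and rate ratios in steps 4 and 5. Against the planned IRRs of 1.45 to 1.90, most such shifts are modest, but they matter more if the true ratio is near 1.

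A reader might infer that the result will wrongly credit infections to ALL therapy. That presumes an estimate of a therapy effect, which the aims do not claim. The supported conclusion is narrower: the plan should show how far the comparison depends on differences it already intends to record.

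**What to change.** In 6.3.2, before control data are pulled:
- Prespecify an IRR adjusted for age, sex, race and ethnicity, reported beside the matched IRR, with a stated rule for unknown race or ethnicity.
- Add a sensitivity analysis that applies the 3.3.3 exclusions to ALL patients for conditions present before, or unrelated to, ALL and its therapy. Conditions caused by ALL or its treatment lie on the pathway and should not trigger exclusion. Remove Down syndrome from both groups in this analysis.
- Use insurance only in a further sensitivity analysis, limited on the ALL side to families who consented to its collection.
- Keep vaccination out of the adjusted model, since it may be a mediator, and report it descriptively.

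In 6.3.4, for the comparison, delete the sentence claiming that a descriptive study cannot be confounded; the next paragraph already describes controlling for confounding. State that site and network differences remain after adjustment.

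The cost is a few sentences and model terms. Race, ethnicity and comorbidity are already listed for both groups, and control data are collected only once ALL follow-up is complete, so the set can be fixed in time. The downside is slightly wider intervals and a small loss of patients in the restricted analysis.
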